## **8.3 Adverse Events and Serious Adverse Events**

### **8.3.1 Definition of Adverse Event (AE)**

AE means any untoward medical occurrence associated with the use of an intervention in humans, whether or not considered intervention-related (21 CFR 312.32 (a)). An AE can therefore be any unfavorable and unintended sign (including an abnormal clinical laboratory finding), symptom or disease temporally associated with the use of medicinal (investigational) product.

Any medical condition that is present at the time that the subject is screened will be considered as baseline and not reported as an AE. However, if the severity of any pre-existing medical condition increases, it should be recorded as an AE.

AEs can be further divided into solicited AEs and unsolicited AEs. Solicited AEs are those for which the study team will specifically query the subject whether they occurred. Unsolicited AEs are those events that the subject report occurring without being queried about the specific event.

All AEs will be assessed for severity and relationship to study intervention ([Section 8.3.3](#)). Reporting of all AEs, solicited and unsolicited, will occur during the period from study product administration on Day 1 through 28 days after the second vaccination. After Day 57 through the end of study on Day 394, only SAEs, Protocol Specified AESIs, MAAEs, and NOCMCs will be reported as AEs.

All AEs, solicited and unsolicited, will be captured on the appropriate DCF. Information to be collected for AEs includes event description, date of onset, assessment of severity, relationship to study product and alternate etiology (assessed only by those with the training and authority to make a diagnosis and listed on the Form FDA 1572 as the participating site PI or appropriate sub-investigator), date of resolution, seriousness, and outcome. AEs occurring during the study-collection and reporting period will be documented appropriately regardless of relationship.

AEs will be followed to resolution or stabilization.

#### **8.3.1.1 Solicited Adverse Events**

Solicited AEs are anticipated local and systemic AEs for which consistent collection of information is desired. Study clinicians will follow and collect resolution information for any reactogenicity symptoms that are not resolved within 7 days.

Solicited AEs (i.e., reactogenicity) will be collected using a memory aid and recorded on the appropriate DCF from the time of each vaccination through 7 days post each vaccination (Days 1-8 for the first vaccination, and Days 29-36 for the second vaccination).

For this study, solicited AEs will be:

- Injection site Pain
- Injection site Erythema
- Injection site Edema/Induration
- Headache
- Fatigue
- Myalgia
- Arthralgia
- Nausea
- Fever
- Chills

#### **8.3.1.2 Unsolicited Adverse Events**

All AEs spontaneously reported by the subject and/or in response to an open question from study staff or revealed by observation, physical examination or other diagnostic procedures must be recorded on the appropriate DCF.

Unsolicited AEs of all severities will be reported from the time of study product administration through Day 57.

After Day 57, only SAEs (as detailed in [Section 8.3.2](#)), Protocol Specified AESIs, MAAEs, and NOCMCs will be reported through the end of the study (Day 394).

#### **8.3.1.3 Possible Adverse Events Associated with Leukapheresis**

For those subjects consented for leukapheresis, the possible adverse events associated with the leukapheresis procedure are:

- Site of needle placement: pain, bruising and discomfort in the arms.
- Vasovagal episodes, characterized by transient hypotension, dizziness, nausea, and rarely syncope.
- Temporary decrease (1-2 days) in red blood cell count.
- Blood loss secondary to machine malfunction.
- Toxicity-associated anticoagulant resulting in a sour taste in the mouth, mild muscle cramps and/or tingling sensation around the mouth, feet or hands.

The risks of the leukapheresis procedure are minimal and are generally confined to the period of the actual study visit itself. In this protocol, AEs that are non-serious will not be routinely recorded in the study database.

Only SAEs that occur during or within 24 hours after the leukapheresis study visit will be recorded in the study database.

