#### **Risks of Leukapheresis (only for those subjects consented for leukapheresis)**

Leukapheresis may be associated with pain, bruising, and discomfort in the arms at the site of needle placement. Vasovagal episodes, characterized by transient hypotension, dizziness, nausea, and rarely syncope, are seen in less than 5% of procedures. Additional risks include increased pulse, seizures, and blood loss. Anticoagulants added to prevent the blood from clotting may lead to a sour taste in the mouth, mild muscle cramps and/or tingling sensation around the mouth, feet or hands. These reactions may be seen to a mild degree in 30-50% of leukapheresis procedures and can usually be relieved by slowing or temporarily interrupting the procedure or administering calcium carbonate tablets.

A temporary decrease (1-2 days) in red blood cell count is common. Rarely, machine malfunction or if the procedure needs to be stopped before completion may result in the loss of a half pint to a pint of blood. Leukapheresis does not affect the blood's ability to form clots in the event of subsequent cuts or injuries.

There may be additional risks that are unknown at this time.

Preclinical evaluations will occur in parallel with this phase I clinical trial. However, in support of the development of mRNA-1273 for prophylaxis against SARS-CoV-2 infection, nonclinical immunogenicity, a Good Laboratory Practice (GLP)-compliant, repeat dose toxicology study, as well as biodistribution and genotoxicity studies have been completed with similar mRNA-based vaccines formulated in SM-102-containing LNPs.

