## 3. OBJECTIVES AND ENDPOINTS

**Table 5: Objectives and Endpoints (Outcome Measures)**

OBJECTIVES	ENDPOINTS (OUTCOME MEASURES)
Primary	

 
To evaluate the safety and reactogenicity of a 2-dose vaccination schedule of mRNA-1273, given 28 days apart, across 5 dosages in healthy adults.
 
	
 
Frequency and grade of each solicited local and systemic reactogenicity AE during a 7-day follow-up period post each vaccination.
 
Frequency and grade of any unsolicited AEs during the 28-day follow-up period post each vaccination.
 
Frequency of any SAEs, Protocol Specified AESIs, NOCMCs, and MAAEs from Day 1 to Day 394.
 

Secondary	

 
To evaluate the immunogenicity as measured by IgG ELISA to the SARS-CoV-2 S (spike) protein following a 2-dose vaccination schedule of mRNA-1273 at Day 57.
 
	
 
GMT of antibody at Day 57.
 
Percentage of subjects who seroconverted, defined as a 4-fold change in antibody titer from baseline.
 
The GMFR in IgG titer from baseline.
 

Exploratory	

OBJECTIVES	ENDPOINTS (OUTCOME MEASURES)

 
To evaluate the immunogenicity as measured by IgG ELISA to the SARS-CoV-2 S (spike) protein following a 2-dose vaccination schedule of mRNA-1273 at all timepoints, other than Day 57.
 
	
 
GMT of antibody at each timepoint.
 
Percentage of subjects who seroconverted at each timepoint.
 
The GMFR in IgG titer from baseline at each post-vaccination timepoint.
 

 
To evaluate the immunogenicity as measured by IgM and IgA ELISA to the SARS-CoV-2 S (spike) protein following a 2-dose vaccination schedule of mRNA-1273 given 28 days apart.
 
	
 
GMT at each timepoint.
 
Percentage of subjects who seroconverted at each timepoint.
 
The GMFR in IgM and IgA titer from baseline at each post-vaccination timepoint.
 

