### **5.1.1 Leukapheresis Inclusion Criteria**

A subject must meet all of the following criteria to be eligible for leukapheresis:

1. Written informed consent for leukapheresis is provided.
2. Weight  $\geq$  110 pounds.
3. Screening laboratory evaluations are within acceptable ranges at the site where the leukapheresis procedure will be performed.
4. Negative urine or serum pregnancy test within 48 hours of the leukapheresis procedure for women of childbearing potential.
5. Adequate bilateral antecubital venous access.
6. No use of blood thinners, aspirin or NSAIDs at least 5 days before the leukapheresis procedure.

7. Enrolled in cohorts 2, 3, 5, 10, or 11, and possibly cohort 6, if enrolled, and completed the two-dose vaccination series.

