#### **8.3.2 Definition of Serious Adverse Event (SAE)**

An SAE is defined in 21 CFR 312.32 as follows: “An AE or suspected adverse reaction is considered serious if, in the view of either the participating site PI or appropriate sub-investigator or the sponsor, it results in any of the following outcomes:

- Death,
- a life-threatening AE,
- inpatient hospitalization or prolongation of existing hospitalization,
- a persistent or significant incapacity or substantial disruption of the ability to conduct normal life functions,
- or a congenital anomaly/birth defect.

Important medical events that may not result in death, be life-threatening, or require hospitalization may be considered serious when, based upon appropriate medical judgment, they may jeopardize the patient or subject and may require medical or surgical intervention to prevent one of the outcomes listed in this definition. Examples of such medical events include allergic bronchospasm requiring intensive treatment in an emergency room or at home, blood dyscrasias or convulsions that do not result in inpatient hospitalization, or the development of drug dependency or drug abuse.”

“Life-threatening” refers to an AE that at occurrence represents an immediate risk of death to a subject. An event that may cause death if it occurs in a more severe form is not considered life-threatening. Similarly, a hospital admission for an elective procedure is not considered an SAE.

All SAEs, as with any AE, will be assessed for severity and relationship to study intervention.

All SAEs will be recorded on the appropriate SAE DCF.

All SAEs will be followed through resolution or stabilization by a study clinician, licensed to make medical diagnoses and listed on the Form FDA 1572 as the participating site PI or appropriate sub-investigator.

All SAEs will be reviewed and evaluated by DMID and will be sent to the SMC (for periodic review unless related) and IRB/IEC.

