#### **8.3.5 Time Period and Frequency for Event Assessment and Follow-Up**

For this study:

- solicited AEs will be collected from Days 1-8 (7 days post first vaccination) and Days 29-36 (7 days post second vaccination).
- unsolicited AEs will be collected from Days 1-57.

- SAEs, Protocol Specified AESIs, MAAEs, and NOCMCs will be collected from Day 1 through the end of the study (Day 394).

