### **8.3.9 Adverse Events of Special Interest (AESIs)**

Adverse Events of Special Interest (AESIs) represent any events for which additional data (besides the standard AE data) are desired. These may be at the request of the regulatory agency, industry partner or DMID, and driven by a regulatory requirement, or known or potential risk from the product or class. Non-structured data similar to SAEs will be collected for AESIs. AESIs encompass the following terms:

- Protocol Specified AESIs:
  - All suspected cases of myocarditis or pericarditis should be recorded. For reporting purposes, a subject who displays signs/symptoms consistent with myocarditis or pericarditis should be reported as a potential case of myocarditis or pericarditis.
- NOCMCs – defined as any new ICD diagnosis (per current International Statistical Classification of Diseases and Related Health Problems) that is applied to the subject during the course of the study, after receipt of the study agent, that is expected to continue for at least 3 months and requires continued health care intervention.
- MAAEs – defined as hospitalization, an emergency room visit or an otherwise unscheduled visit to or from medical personnel for any reason.

All AESIs are assessed, recorded, and followed as described above under AEs. AESIs that meet SAE criteria will be reported on an SAE form within 24 hours to the DMID Pharmacovigilance Group, at the following address:

DMID Pharmacovigilance Group  
Clinical Research Operations and Management Support (CROMS)  
[name]  
[name]  
SAE Hot Line: [name] (US) or [name] (outside US)  
SAE [contact] (US) or [name] (outside US)  
SAE Email Address: [[contact]](mailto:[contact])

In addition, for documentation and medical assessment purposes AESIs that do not meet SAE criteria will also be reported on an SAE form within the period for AE reporting to the DMID Pharmacovigilance Group; however, the narrative will indicate that the AESI did not meet SAE criteria.

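### Protocol section 8.3.1.3 limits recording of leukapheresis-associated events to SAEs within 24 hours, which conflicts with a primary endpoint that counts every SAE, AESI, NOCMC and MAAE to Day 394

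*Protocol*

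**What the plan says.** Section 8.3.1.3 lists the events that may follow leukapheresis, calls the risks minimal, and sets two recording limits. On non-serious events: "In this protocol, AEs that are non-serious will not be routinely recorded in the study database". On serious events: "Only SAEs that occur during or within 24 hours after the leukapheresis study visit will be recorded in the study database". It makes no exception for MAAEs, NOCMCs or AESIs and does not refer to the general collection rules.

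Those rules are cause-blind. The third primary safety endpoint (Protocol Table 5) is "Frequency of any SAEs, Protocol Specified AESIs, NOCMCs, and MAAEs from Day 1 to Day 394". Section 8.3.2 says "All SAEs will be recorded on the appropriate SAE DCF". Section 8.3.5 gives the period for the four classes as Day 1 to Day 394, and section 8.3.1.2 gives the same end date. Section 8.3.9 defines an MAAE as "defined as hospitalization, an emergency room visit or an otherwise unscheduled visit to or from medical personnel for any reason". Section 8.3.1 requires events in the reporting period to be documented whether or not they are related to vaccine, and section 8.3.7.1 requires selected SAE fields to go into the coordinating center's system as well as onto the SAE form.

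Section 5.1.1 restricts the procedure to subjects "Enrolled in cohorts 2, 3, 5, 10, or 11, and possibly cohort 6, if enrolled, and completed the two-dose vaccination series". Cohort 6 was not enrolled. SAP section 4.1 reports that subsets of the other five cohorts have had the procedure.

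**The concern.** The two sets of instructions give different answers for the same event. Take a subject who goes to an emergency room after the visit with a procedure-related complaint and is not admitted. Under 8.3.9 that is an MAAE, so it counts in a primary endpoint. Under 8.3.1.3 it is a non-serious procedure event and is not routinely recorded. Likewise, a procedure-associated hospitalization that begins on the third day after the visit is an SAE under 8.3.2 and 8.3.5 but falls outside the 24-hour window of 8.3.1.3. Both examples are illustrations, not events described in the documents.

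What is at stake is completeness of a primary endpoint. The count for affected subjects depends on which section the site applied, and the final data cannot show which that was, because an unrecorded event leaves no trace. Since no 25 mcg cohort is eligible, any loss would occur only at the three higher doses.

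**Working it through.** The plan gives no figure for this point, so the check compares the rules and then does date and cohort arithmetic.

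**1. Rules side by side, for an event associated with leukapheresis**

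| Event | Section 8.3.1.3 | Table 5 and sections 8.3.1.2, 8.3.2, 8.3.5, 8.3.9 |
|---|---|---|
| SAE during the visit or within 24 hours | recorded | recorded |
| SAE starting after 24 hours | not recorded | recorded to Day 394 |
| Non-serious MAAE, NOCMC or AESI | not routinely recorded | recorded to Day 394 |
| Other non-serious event | not routinely recorded | not collected after Day 57 |

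The conflict is in rows two and three only.

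**2. Timing**

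Inputs: Visit 11A is Day 71, minus 7 to plus 21 days (Protocol Table 4). Ordinary unsolicited collection ends at Day 57 (8.3.1.2). Endpoint follow-up ends at Day 394.

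- Procedure window: 71 − 7 = Day 64 to 71 + 21 = Day 92.
- Days after ordinary unsolicited collection ends: 64 − 57 = 7 to 92 − 57 = 35.
- The 24-hour window closes on Day 65 to Day 93.
- Days left to Day 394 in which a procedure-associated SAE would go unrecorded: 394 − 93 = 301 to 394 − 65 = 329.

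These are nominal days. The windows run from the actual second-dose visit, which may move by 2 days. Even at the earliest, 64 − 2 = Day 62 is still after Day 57.

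The timing explains why row four is harmless. It also shows what the non-serious clause does in practice. By Visit 11A the only non-serious events still being collected are MAAEs, NOCMCs and AESIs, so the clause either has no effect or removes events from those endpoint classes.

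**3. Who can be affected**

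Inputs: cohort sizes from Protocol Table 6; eligible cohorts from section 5.1.1.

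- Eligible: 15 + 15 + 10 + 15 + 10 = 65 of 120 (cohorts 2, 3, 5, 10, 11).
- By dose: 25 mcg 0/35; 50 mcg (15 + 10)/35 = 25/35; 100 mcg (15 + 10)/35 = 25/35; 250 mcg 15/15.
- By age: 18-55, 45/60; 56-70, 20/30; 71 or over, 0/30.

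These are upper limits, because only a consenting subset has the procedure and its size is not given.

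**4. Effect of one omitted subject**

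The percentage of subjects with an event changes by 1/15 = 6.7 points in a cohort of 15 and by 1/10 = 10 points in a cohort of 10.

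**The case against.** The strongest reply is that 8.3.1.3 is about the procedure and not about the subject. Its heading and opening sentence confine it to events associated with leukapheresis. Applied to everything that happens to these subjects, it would also cancel solicited and unsolicited collection, which cannot be meant. Section 8.2 still requires interim histories at later visits to look for AESIs, MAAEs and NOCMCs. This stands, and it sets the scope of the point. It does not remove the conflict, because the endpoint has no cause restriction and procedure-associated events in the four classes belong in it.

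Three stronger readings are tempting, and the documents do not support them.

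- A reader might infer that surveillance of leukapheresis subjects stops after 24 hours. It does not, for the reasons just given.
- A reader might infer that recorded procedure events inflate the higher-dose arms and bias the dose comparison. Recording an any-cause event in an any-cause endpoint is not inflation. The trial is non-randomized and tests no hypothesis (Protocol 6.3.2 and 9.1), and the documents do not name 25 mcg as a reference. Attribution is also available: section 8.3.1 collects relationship and alternate etiology, SAP section 9.4 specifies both for the SAE listing and for the MAAE/NOCMC listing, and SAP Tables 138 to 140 split SAEs by relationship. Table 140 covers ages 71 and over and is unaffected. The MAAE row in Tables 138 to 140 has no such split, but that is a limit of display.
- A reader might take the protocol's statement that vasovagal episodes "are seen in less than 5% of procedures" as the size of the problem: 65 × 5% = 3.25. That number describes the wrong event. A transient episode during a scheduled visit is neither an SAE nor, in itself, an MAAE, and 65 is the number eligible, not the number treated.

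**Conclusion.** Section 8.3.1.3 is wrong as written and should be corrected, within a narrow scope. It conflicts with the primary endpoint for procedure-associated SAEs starting more than 24 hours after the visit and for procedure-associated MAAEs, NOCMCs and AESIs. Followed literally, it drops such events from that endpoint.

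The size is modest. At most 65 of 120 subjects are exposed, none of them at 25 mcg and none aged 71 or over, so any under-recording falls only in the 50, 100 and 250 mcg arms. The expected number of events is small, but it cannot be calculated: the documents give neither the number of procedures nor the share that leads to a medical contact or a late SAE.

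The conclusion assumes that at least some sites would read 8.3.1.3 as overriding the general rules for procedure events. If every site applied 8.3.5 and 8.3.9, nothing would be lost, but the protocol does not say which section prevails.

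**What to change.** Reconcile section 8.3.1.3 with 8.3.5 and 8.3.9. State that its recording limit applies only to procedure-associated events that are not SAEs, Protocol Specified AESIs, MAAEs or NOCMCs. State also that events in those four classes are recorded to Day 394 as for all other subjects, and refer to 8.3.5 and 8.3.9. Because the procedure has already been carried out in some subjects, sites should be asked whether any such event was left out under the present wording, and should add it before the final data lock.

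The cost is one sentence, one query to at most three sites, and a few more recorded events. No sample-size figure or analysis method changes. A leukapheresis flag on the event record, with SAE and MAAE counts shown with and without flagged events, is optional, since relationship and alternate etiology are already collected and listed.

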#### **8.3.1.4 Special Reporting of Adverse Events**

Not Applicable

#### **8.3.2 Definition of Serious Adverse Event (SAE)**

An SAE is defined in 21 CFR 312.32 as follows: “An AE or suspected adverse reaction is considered serious if, in the view of either the participating site PI or appropriate sub-investigator or the sponsor, it results in any of the following outcomes:

- Death,
- a life-threatening AE,
- inpatient hospitalization or prolongation of existing hospitalization,
- a persistent or significant incapacity or substantial disruption of the ability to conduct normal life functions,
- or a congenital anomaly/birth defect.

Important medical events that may not result in death, be life-threatening, or require hospitalization may be considered serious when, based upon appropriate medical judgment, they may jeopardize the patient or subject and may require medical or surgical intervention to prevent one of the outcomes listed in this definition. Examples of such medical events include allergic bronchospasm requiring intensive treatment in an emergency room or at home, blood dyscrasias or convulsions that do not result in inpatient hospitalization, or the development of drug dependency or drug abuse.”

“Life-threatening” refers to an AE that at occurrence represents an immediate risk of death to a subject. An event that may cause death if it occurs in a more severe form is not considered life-threatening. Similarly, a hospital admission for an elective procedure is not considered an SAE.

All SAEs, as with any AE, will be assessed for severity and relationship to study intervention.

All SAEs will be recorded on the appropriate SAE DCF.

All SAEs will be followed through resolution or stabilization by a study clinician, licensed to make medical diagnoses and listed on the Form FDA 1572 as the participating site PI or appropriate sub-investigator.

All SAEs will be reviewed and evaluated by DMID and will be sent to the SMC (for periodic review unless related) and IRB/IEC.

#### **8.3.3 Suspected Unexpected Serious Adverse Reactions (SUSAR)**

A SUSAR is any SAE where a causal relationship with the study product is at least reasonably possible but is not listed in the Investigator’s Brochure (IB), Package Insert, and/or Summary of Product Characteristics.

#### **8.3.4 Classification of an Adverse Event**

The determination of seriousness, severity and causality will be made by an on-site investigator who is qualified (licensed) to diagnose AE information, provide a medical evaluation of AEs and classify AEs based upon medical judgment. This includes, but is not limited to, physicians, physician assistants and nurse practitioners.

